5.8. CTCAE Grading

Grading Criteria for Clinical Laboratory Tests [CTCAE Version 5.0]					
Hematology Tests		Criteria			
Test	Direction	1	2	3	4
Hemoglobin (g/L)	Decrease	≥ 100 - <LLN	≥ 80 - <100.0	<80	
Leukocytes (WBC) ($10^9/L$)	Decrease	≥ 3.0 - <LLN	≥ 2.0 - <3.0	≥ 1.0 - <2.0	<1.0
Lymphocytes ($10^9/L$)	Decrease	≥ 0.8 - <LLN	≥ 0.5 - <0.8	≥ 0.2 - <0.5	<0.2
Neutrophils ($10^9/L$)	Decrease	≥ 1.5 - <LLN	≥ 1.0 - <1.5	≥ 0.5 - <1.0	<0.5
Platelets ($10^9/L$)	Decrease	≥ 75.0 - <LLN	≥ 50.0 - <75.0	≥ 25.0 - <50.0	<25.0
Chemistry Tests		Criteria			
Test	Direction	1	2	3	4
ALT	Increase	>ULN - ≤ 3.0 Xuan if baseline was normal; 1.5 - 3.0 x baseline if baseline was abnormal	>3.0 xULN - ≤ 5.0 xULN if baseline was normal; >3.0 - 5.0 x baseline if baseline was abnormal	>5.0 xULN - ≤ 20.0 xULN if baseline was normal; >5.0 - 20.0 x baseline if baseline was abnormal	>20.0 xULN if baseline was normal; >20.0 x baseline if baseline was abnormal
Albumin (g/L)	Decrease	≥ 30 - <LLN	≥ 20 - <30	<20	
Alkaline Phosphatase	Increase	>ULN - ≤ 2.5 xULN if baseline was normal; 2.0 - 2.5 x baseline if baseline was abnormal	>2.5 xULN - ≤ 5.0 xULN if baseline was normal; >2.5 - 5.0 x baseline if baseline was abnormal	>5.0 xULN - ≤ 20.0 xULN if baseline was normal; >5.0 - 20.0 x baseline if baseline was abnormal	>20.0 xULN if baseline was normal; >20.0 x baseline if baseline was abnormal

AST	Increase	>ULN - ≤ 3.0 xULN if baseline was normal; 1.5 - 3.0 x baseline if baseline was abnormal	>3.0 xULN - ≤ 5.0 xULN if baseline was normal; >3.0 - 5.0 x baseline if baseline was abnormal	>5.0 xULN - ≤ 20.0 xULN if baseline was normal; >5.0 - 20.0 x baseline if baseline was abnormal	>20.0 xULN if baseline was normal; >20.0 x baseline if baseline was abnormal
Bilirubin	Increase	>ULN - ≤ 1.5 xULN if baseline was normal; > 1.0 - 1.5 x baseline if baseline was abnormal	>1.5 xULN - ≤ 3.0 xULN if baseline was normal; >1.5 - 3.0 x baseline if baseline was abnormal	>3.0 xULN - ≤ 10.0 xULN if baseline was normal; >3.0 - 10.0 x baseline if baseline was abnormal	>10.0 xULN if baseline was normal; >10.0 x baseline if baseline was abnormal
Calcium (mmol/L)	Increase	>ULN - ≤ 2.9	>2.9 - ≤ 3.1	>3.1 - ≤ 3.4	>3.4
Calcium (mmol/L)	Decrease	[Albumin ≥ 40 g/L or missing and calcium ≥ 2.0 - $< LLN$]; or [Albumin < 40 g/L and (calcium - 0.8 x (albumin - 40)) ≥ 2.0 - $< LLN$]	[Albumin ≥ 40 g/L or missing and calcium ≥ 1.75 - < 2.0]; or [Albumin < 40 g/L and (calcium - 0.8 x (albumin - 40)) ≥ 1.75 - < 2.0]	[Albumin ≥ 40 g/L or missing and calcium ≥ 1.5 - < 1.75]; or [Albumin < 40 g/L and (calcium - 0.8 x (albumin - 40)) ≥ 1.5 - < 1.75]	[Albumin ≥ 40 g/L or missing and calcium < 1.5]; or [Albumin < 40 g/L and (calcium - 0.8 x (albumin - 40)) < 1.5]
Creatinine	Increase	>ULN - ≤ 1.5 xULN	>1.5 xULN - ≤ 3.0 xULN	>3.0 xULN - ≤ 6.0 xULN	>6.0 xULN
GGT	Increase	>ULN - 2.5 x ULN if baseline was normal; 2.0 - 2.5 x baseline if baseline was abnormal	>2.5 - 5.0 x ULN if baseline was normal; >2.5 - 5.0 x baseline if baseline was abnormal	>5.0 - 20.0 x ULN if baseline was normal; >5.0 - 20.0 x baseline if baseline was abnormal	>20.0 x ULN if baseline was normal; >20.0 x baseline if baseline was abnormal
Phosphate (mmol/L)	Decrease	≥ 0.8 - $< LLN$	≥ 0.6 - < 0.8	≥ 0.3 - < 0.6	< 0.3
Potassium (mmol/L)	Increase	>ULN - ≤ 5.5	>5.5 - ≤ 6.0	>6.0 - ≤ 7.0	>7.0
Potassium (mmol/L)	Decrease	≥ 3.0 - $< LLN$		≥ 2.5 - < 3.0	< 2.5
Sodium (mmol/L)	Increase	>ULN - ≤ 150	>150 - ≤ 155	>155 - ≤ 160	>160
Sodium (mmol/L)	Decrease	≥ 130 - $< LLN$		125-129 mmol/L symptomatic; 120-	< 120

				124 mmol/L regardless of symptoms	
--	--	--	--	---	--

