4.1. Inclusion Criteria

100. Subject is willing and able to provide written, signed informed consent at Screening Part 1 prior to start of any study-related procedures
101. Subject is a male or female at least 18 years of age at the time of Screening
102. Subject has a diagnosis of CD with involvement of at least the ileum or any portion of the colon at a minimum, diagnosed by radiology, endoscopy, and/or histology at least 3 months prior to Screening. The report of a previous diagnostic exam (endoscopy, radiology, and/or pathology) must be reviewed by the investigator and included in the source documents.
103. Subjects must have up-to-date colorectal cancer screening as per locally adopted guidelines (e.g., if subject has had ≥ 8 years of disease involving $>30\%$ of the colon, surveillance biopsies or chromoendoscopy should be performed if either is indicated as per locally adopted guidelines but has not been performed within the 12 months prior to Screening). If indicated, the surveillance biopsies (if ≥ 10) and chromoendoscopy need to be performed during Screening Stage 2 ileocolonoscopy after recording of a full ileocolonoscopy has been completed to avoid dye or biopsy-related bleeding artifact on the recorded images.
104. Subject has CDAI score ≥ 220 and ≤ 450
105. Subject has a SES-CD score of ≥ 3 with ulceration (corresponding to a score of ≥ 1) in at least 1 of the 5 ileocolonic segments on the Ulcerated Surface subscore of the SES-CD, as assessed by central reading, during Screening
 - a. Up to approximately 10% of the study population will have SES-CD score of between 3 and 5, inclusive, with the presence of ulceration in any 1 of the 5 ileocolonic segments, all other subjects (approximately 90% of the study population) will require an SES-CD score of ≥ 6 (≥ 4 if isolated ileal disease) with ulceration (corresponding to a score of ≥ 1) in at least 1 of the 5 ileocolonic segments on the Ulcerated Surface subscore of the SES-CD
106. Subject is corticosteroid-dependent or had intolerance or inadequate response to any of the following: aminosalicylates, corticosteroids, immunomodulators (azathioprine, 6-mercaptopurine, or methotrexate), or biologics (anti-TNF anti-IL-12/IL-23 therapy, or anti-integrin) [Refer to [Appendix 10](#)]

NOTE: For subjects in **Portugal**, subject must have had intolerance or inadequate response to biologics

107. If subject is currently receiving an oral corticosteroid, subject is eligible if:

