3.2.2. Demographic and Baseline Characteristics

Demographics

Demographic data including age, sex, race, ethnicity, weight, height, and body mass index (BMI) will be summarized overall and by treatment group. Sex, race, and ethnicity frequency distributions will be provided. Age will be further categorized as 18 to 64 vs. ≥ 65 years.

Tobacco Consumption

A summary of Tobacco Consumption taken at baseline or screening will be provided summarizing:

Parameter	Units/Response category
Tobacco Consumption Status	Never, Current, Former
Number of Tobacco Units Per Day	Converted Units
Number of Years With Tobacco Use	Years
Total Number Of Pack Years	Pack Years
Type of Tobacco Product Used	Cigarettes, Cigars, Pipe, Smokeless Tobacco

The following conversion process is used to standardize a unit of tobacco consumption:

1 unit = 1 pack (20 cigarettes) = 5 cigars = 8 pipes = 8 pinches

Number of years of tobacco use is calculated as follows where current smokers use the Day 1 Visit date as end date:

$$\frac{(\text{Tobacco use end date} - \text{Tobacco use start date} + 1)}{365.25}$$

Pack Years is calculated as number of years of tobacco use multiplied by number of tobacco units per day (converted units).

A listing will also be provided.

Crohn's Disease Clinical Characteristics

A summary of Crohn's Disease Clinical Characteristics taken at baseline or screening will be provided. A listing will also be provided.

Parameter	Units/Response category
Time since diagnosis of Crohn's disease	Years
Time Since Diagnosis categories	≤ 5years; >5 to ≤15 years; > 15 years
Extent of disease	Ileal, Colonic, Ileocolonic
Baseline CDAI score	Points
Baseline CDAI score categories	≤300 points, >300 points
Baseline Abdominal Mass	None, Questionable, Definite
Baseline average daily Abdominal Pain	None, Mild, Moderate, Severe
Baseline average daily liquid or very soft Stool Frequency	Stools
Baseline average daily total Stool Frequency	Stools
Baseline SES-CD score	Points
Upper GI Crohn's	Yes, No
██████████	██████
████████████████████	██████
██████████	
██████████████████	██████
████████████████████	██████
██████████████████	
████████████████████	██████
██████████████████	██████

Prior Crohn's Disease Therapy Characteristics

A summary of Prior Crohn's Disease Therapy Characteristics will be provided. A listing will also be provided.

Parameter	Units/Response category
Prior biologic failure	Yes, No
Prior biologic experience	Failed, Naïve, Experienced but no documented failure

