3.3.6.3. Subgroup Analysis

To characterize the consistency of the treatment effect for the primary and supplementary estimands, the primary endpoint analysis will be repeated for each examination group specified below.

The subgroups will be analyzed with the inclusion of a 3-way interaction term treatment*visit*subgroup category into the primary analysis model. The exceptions are, (1) baseline CDAI category (≤ 300 , > 300) where along with the inclusion of the of a 3-way interaction term treatment*visit*[baseline CDAI category (≤ 300 , > 300)], the baseline continuous CDAI score is replaced in the primary analysis model with the baseline CDAI category and (2) subgroups listed (2-5) below where prior biologic failure in the model is replaced with the subgroup along with the addition of the 3 way interaction term.

The following subgroups at baseline are pre-defined:

1. Biologic Failure Status: [a] Yes, [b] No
(definition see section 5.3.1.7)
2. Biologics experience categories: [a] Failed, [b] naïve, [c] bio-experienced [but not failed]
3. Number of prior biologics failed [a] 0 [b] 1 [c] 2 [d] ≥ 3
4. Number of biologic mechanism of actions failed [a] 0 [b] 1 [c] 2 [d] 3
5. Intolerant to at least one biologic: [a] Yes, [b] No
6. Baseline CDAI category: [a] ≤ 300 pts, [b] > 300 pts
7. Tobacco use Status: [a] no use, [b] prior use, [c] current use
8. Extent of disease: [a] Ileal, [b] Colonic, [c] Ileocolonic
9. Age: [a] ≤ 40 years, [b] > 40 years
10. Duration of disease: [a] ≤ 5 years, [b] > 5 to ≤ 15 years, [c] > 15 years
11. Age at diagnosis: [a] \leq median, [b] $>$ median
12. Baseline Fistula: [a] Yes, [b] No
-
-
15. Baseline SES-CD score: [a] \leq median, [b] $>$ median
16. Presence of extra-intestinal manifestations at baseline: [a] Yes, [b] No

17. Corticosteroid-use at baseline: [a] Yes, [b] No
18. Refractory or intolerant to 6-MP/AZA: (yes, no)
19. Refractory or dependent to oral or IV corticosteroids: (yes, no)
20. Refractory, intolerant or dependent to 6-MP/AZA OR corticosteroids: [a] yes to both, [b] No to 6-MP/AZA and yes to steroids, [c] yes to 6-MP/AZA and no to steroids, [d] No to both
21. History of intestinal resection: [a] Yes, [b] No
22. Geographic Region: [a] North America [b] Eastern Europe [c] Europe (excluding Eastern Europe)[d] Other;

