3.7.3. Additional Safety Assessments

3.7.3.1. Clinical Laboratory Parameters

Laboratory data, hematology, serum chemistry and urinalysis, will be summarized in terms of observed values and changes from baseline for Induction period and overall separately. In addition, changes from baseline relative to normal ranges from the central lab (e.g., shifts from normal to abnormal high/low) will be summarized.

Summaries for laboratory parameters of special interest will also be presented, these will include:

- Neutrophils
- Leukocytes
- Lymphocytes
- Hemoglobin
- Lipids [LDL cholesterol, HDL cholesterol, Cholesterol, and Triglyceride]
- Liver Function Test's [ALT, AST, Bilirubin]
- Creatinine
- Creatinine Kinase

A summary of maximum National Cancer Institute Common Terminology Criteria for Adverse Events (NCI-CTCAE) toxicity grade (Appendix 5.8) for postbaseline laboratory values through Week 12 and ATE Week 48.

Listings will flag laboratory values that are outside of normal range.

A listing of all abnormal lab values will be provided. Listings of subjects with any abnormal postbaseline laboratory values of CTCAE grade ≥ 2 will also be provided.

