5.3.1.6. Time Since Crohn’s Disease Diagnosis

Time since CD diagnosis (years) as of the first dose date is calculated as (diagnosis date - first dose date)/365.25. It is left unrounded for calculation of summary statistics but rounded to 1 decimal place for display.

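### Three SAP derivation rules give wrong results as written (none affects the primary test): albumin-corrected calcium grading, time since diagnosis, and year-only medication start dates

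*SAP*

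**What the plan says.** **(a) Calcium.** The table in SAP 5.8 labels the row "Calcium (mmol/L") and gives albumin in g/L. If albumin is 40 or more, or missing, measured calcium is graded directly. Below 40, each of the four low-calcium cells applies the same correction; the Grade 4 cell is "Albumin < 40 g/L and (calcium - 0.8 x (albumin - 40)) < 1.5". SAP 3.7.3.1 uses the grades in a maximum-grade summary and in "Listings of subjects with any abnormal postbaseline laboratory values of CTCAE grade" 2 or higher. It also states: "Listings will flag laboratory values that are outside of normal range".

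**(b) Time since diagnosis.** SAP 5.3.1.6 computes it as "diagnosis date - first dose date)/365.25" (the quote starts after the opening bracket). The baseline table in SAP 3.2.2 has a row "Time Since Diagnosis categories" with cut-points at 5 and 15 years. Subgroup 10 in SAP 3.3.6.3, disease duration, uses the same cut-points. Inclusion criterion 102 in Protocol 4.1 requires Crohn's disease "diagnosed by radiology, endoscopy, and/or histology at least 3 months prior to Screening".

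**(c) Medication start dates.** SAP 5.3.2.3 is meant to tell use before dosing from use after it. When only the year of a start is known, it imputes 31 December, or the study exit date if that is in the same year and earlier. SAP 5.3.2.2 gives this same rule for end dates. When month and year are known, 5.3.2.3 imputes the first of the month, or the first dose date if that is in the same month and later.

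**The concern.** Each rule returns a value that cannot be what was intended. In (a) the coefficient does not fit the units beside it, and the error hides low calcium. In (b) a duration comes out negative. In (c) the latest possible date is used for a start.

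At stake are the calcium grades in the safety tables, the disease-duration rows of the baseline table (and the duration subgroup, if it uses the same variable), and the prior and concomitant medication tables of SAP 3.2.5. Errors (a) and (c) would not stand out in the output: an over-corrected calcium simply goes ungraded, and each imputed date is a valid date.

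**Working it through.** The plan states no derived figure for these rules, so there is nothing to reproduce first. Each rule is evaluated as written.

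**(a) Calcium.** Inputs from SAP 5.8: corrected calcium = measured − 0.8 × (albumin − 40) when albumin is below 40. Grade 2 or higher means corrected calcium below 2.0, and Grade 4 means below 1.5. The amount added is therefore 0.8 × (40 − albumin). Measured calcium must lie below 2.0 minus that amount for Grade 2 or higher, and below 1.5 minus that amount for Grade 4.

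| Albumin (g/L) | Added (mmol/L) | Grade 2 or higher needs measured calcium below | Grade 4 needs measured calcium below |
|---|---|---|---|
| 39.5 | 0.4 | 1.6 | 1.1 |
| 39 | 0.8 | 1.2 | 0.7 |
| 38.125 | 1.5 | 0.5 | 0 (impossible) |
| 38 | 1.6 | 0.4 | impossible |
| 37.5 | 2.0 | 0 (impossible) | impossible |
| 35 | 4.0 | impossible | impossible |

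The two limits are 40 − 1.5/0.8 = 38.125 for Grade 4 and 40 − 2.0/0.8 = 37.5 for Grade 2 or higher.

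Example: a measured 1.4 mmol/L is Grade 4 at albumin 40. At albumin 35 it becomes 1.4 + 0.8 × 5 = 5.4 and gets no low grade. The 4.0 added is by itself above the same table's Grade 4 cut-off for high calcium, 3.4. The albumin row of the table grades values below 30 and below 20 g/L, so low albumin is foreseen.

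Size of a consistent correction (assumption): if 0.8 was meant in mg/dL per g/dL, then with about 0.25 mmol/L per mg/dL and 10 g/L per g/dL the coefficient is 0.8 × 0.25 / 10 = 0.02. At albumin 35 it adds 0.10, and 1.4 becomes 1.50 (Grade 3). Over half to double that coefficient (0.01 to 0.04) it adds 0.05 to 0.20, giving 1.45 (Grade 4) to 1.60 (Grade 3). The subject is graded throughout this range. As written, the subject is not graded.

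**(b) Time since diagnosis.** Diagnosis precedes Screening by at least 3 months, about 91/365.25 = 0.25 years, so every value is about −0.25 or lower. Diagnosis 2, 10 and 20 years before first dose gives −2, −10 and −20. All satisfy the 5-years-or-less condition, and the other two categories are empty. With the subtraction turned round, the three subjects fall in the three separate categories.

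**(c) Medication start.** Illustration with first dose on 10 March 2020:

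- Start recorded as 2020: imputed as 1 July 2020 if study exit is that day, or 31 December 2020 if exit is in 2021. If the drug was stopped before 10 March, its start now follows its stop.
- Start recorded as 2018: imputed as 31 December 2018, still before dosing.
- Start recorded as March 2020 and stopped before 10 March: the month-known bullet imputes 10 March, again after the stop.

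A year-only start in the exit year can become the exit date. SAP 3.2.5 leaves out of its summaries any medication starting more than 28 days after last dose. If study exit is the End of Study visit (assumption; no visible text defines the exit date), Protocol 6.3.14 with the −3 to +5 day window of Protocol 6 allows up to 28 + 5 = 33 days after last dose. For early discontinuation, Protocol 3.1 counts the 4 weeks from a visit up to 5 days after last dose, so the limit is about 5 + 28 + 5 = 38 days. In either case the imputed start can pass the 28-day limit and the drug drops out.

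**The case against.** The best case on the other side is that these are drafting slips with little reach. Calcium is not among the laboratory parameters of special interest in SAP 3.7.3.1, out-of-range raw values are still flagged, negative durations would be seen in the first baseline table, and the documents give no frequency of year-only starts. All of this stands and sets the priority. It does not make the rules right, and a programmer who corrects them silently departs from the SAP.

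Several stronger readings are tempting but not supported:

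- *Low calcium would be reported as severe high calcium.* The Increase row in SAP 5.8 grades uncorrected calcium. The error removes low grades and creates no high ones.
- *The duration subgroup is broken.* SAP 3.3.6.3 does not cite 5.3.1.6. The matching cut-points suggest the same variable but do not establish it.
- *The end-date rule is what turns a pre-dose drug into a concomitant one, and the AE start rule would cure it.* In the first-dose year, a rule like that of SAP 5.3.2.1 gives the first dose date, so the class is the same. That rule is also justified only for treatment-emergent events, so its difference from the medication rule is not in itself a contradiction.
- *False intercurrent events would follow, above all new corticosteroid or aminosalicylate use, and reach Supplementary Estimand 1 and the binary secondary endpoints.* No visible text uses imputed medication dates to define intercurrent events, and the material between SAP 5.4 and 5.8 is redacted.

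**Conclusion.** All three rules are wrong as written. Parts (a) and (b) follow from the SAP's own units, cut-offs and dates. Only the size of the right calcium correction rests on an assumption. Part (c) is a duplicated end-date rule with two visible effects: a start later than the drug's own stop, and possible loss of a drug from the medication summary. The second depends on study exit falling more than 28 days after last dose. The month-known bullet shares the first effect in the first-dose month.

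A reader might infer that the primary result is at risk. It is not: the primary estimand in SAP 3.3.4.1 follows a treatment policy strategy, and the model in SAP 3.3.4.2 uses none of these variables. The reach is descriptive safety, baseline and medication tables, plus one subgroup if it uses the 5.3.1.6 variable. Low priority, but worth correcting before database lock.

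**What to change.** 1. **Calcium (SAP 5.8):** in all four low-calcium cells, use a coefficient consistent with mmol/L and g/L. That is 0.02 if 0.8 was meant in mg/dL per g/dL, which the sponsor should confirm.
2. **Time since diagnosis (SAP 5.3.1.6):** use (first dose date − diagnosis date)/365.25, and state in SAP 3.3.6.3 whether subgroup 10 uses this variable.
3. **Medication start (SAP 5.3.2.3):** replace the year-only bullet with a start-date rule, and cap the imputed start at the recorded stop date in both the year-only and the month-known bullets. Let CRF status (ongoing at baseline, or stopped before first dose) decide pre-dose use. State that no medication counts as an intercurrent event on an imputed date alone.

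The cost is three short text corrections and their programming, with no new data collection. One limit remains: a first-dose-year start with neither a pre-dose stop nor a CRF record of baseline use may still be classed as post-dose.

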6.4.12. Chemistry, Hematology, and Urinalysis

Laboratory assessments will be performed as specified in Schedule of Study Procedures (Table 1).

Additional and repeat laboratory safety testing for the evaluation of abnormal results and/or adverse events during the study may be performed at the discretion of the investigator or upon request of the Sponsor. Repeat laboratory testing of abnormal potentially clinically significant or clinically significant results for Screening evaluation of the subject may be repeated at the discretion of the investigator.

Chemistry samples will be analyzed for the following: sodium, potassium, calcium, magnesium, chloride, bicarbonate, glucose, blood urea nitrogen, creatinine, total bilirubin, direct and indirect bilirubin, total protein, albumin, alkaline phosphatase, lactate dehydrogenase, ALT, AST, gamma-glutamyl transferase, and creatine phosphokinase.

Hematology samples will be analyzed for the following: hematocrit and hemoglobin; red blood cell count; mean corpuscular volume; mean corpuscular hemoglobin; mean corpuscular hemoglobin concentration; reticulocyte count; white blood cell count, including differential count (percent and absolute) of neutrophils, eosinophils, basophils, monocytes, lymphocytes; and platelet count.

Urinalysis includes determination of specific gravity; presence of blood, glucose, protein, nitrite, and leukocytes; and microscopic examination of sediment, if clinically indicated.

Detailed instructions and collection kits for sample collection, handling, and shipping will be provided by the central laboratory.

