6.4.13. Overnight Fasting Lipid Panel

Fasting low-density lipoprotein (LDL), high-density lipoprotein (HDL), triglyceride, and total cholesterol will be measured at the time points designated in Schedule of Study Procedures (Table 1). Subject must fast from food and non-clear fluids for a minimum of 8 hours overnight prior to blood collection.

Detailed instructions and collection kits for sample collection, handling, and shipping will be provided by the central laboratory.

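### The sodium-decrease row in SAP 5.8 gives no toxicity grade to a value of 125-129 mmol/L without symptoms, although values on both sides of that band are graded

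*SAP*

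**What the plan says.** SAP 3.7.3.1 (Clinical Laboratory Parameters) plans "A summary of maximum National Cancer Institute Common Terminology Criteria for Adverse Events (NCI-CTCAE) toxicity grade" for post-baseline results, through Week 12 and through ATE Week 48, using the table in SAP 5.8. It also plans a listing of subjects with any post-baseline result of grade 2 or higher.

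The sodium-decrease row in SAP 5.8 reads:

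- Grade 1: from 130 mmol/L up to, but not including, the LLN.
- Grade 2: empty.
- Grade 3: "125-129 mmol/L symptomatic", or 120 to "124 mmol/L regardless of symptoms".
- Grade 4: below 120 mmol/L.

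Neither section says where symptom status is to be found, or what to do with a value of 125-129 when no symptoms are recorded.

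**The concern.** A grading scale should not lose a result as it gets worse. Here, as sodium falls without symptoms, the grade goes from 1 to nothing, then to 3, then to 4. The wording for 120-124 makes clear that symptoms are a deliberate condition on the 125-129 band, so the symptom-free case is a real branch of the rule, and that branch has no outcome.

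Safety and tolerability is one of the two primary objectives, and the maximum-grade summary and the grade 2 or higher listing are the outputs in which laboratory severity is graded. A programmer who meets a symptom-free 127 mmol/L has to choose between no grade, Grade 2 and Grade 3, and the SAP supports none of these. That choice should be fixed before the tables are programmed.

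**Working it through.** There is no figure in the plan to reproduce. The check applies the printed row to every possible value.

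**Inputs** (all from SAP 5.8, sodium decrease): Grade 1 at 130 to below LLN; Grade 2 empty; Grade 3 at 125-129 with symptoms or 120-124 in any case; Grade 4 below 120. An LLN of 135 mmol/L is assumed for illustration. The result is the same for any LLN of 130 or more, because the LLN only sets the upper edge of Grade 1.

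**Result**, for whole-number sodium values:

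| Sodium (mmol/L) | Grade with symptoms | Grade without symptoms |
|---|---|---|
| 130-134 | 1 | 1 |
| 125-129 | 3 | none |
| 120-124 | 3 | 3 |
| below 120 | 4 | 4 |

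The ungraded band holds 129 - 125 + 1 = 5 whole-number values.

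**Effect on the two outputs.**

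- Subject A has 132 and later 127 mmol/L, no symptoms. The 132 is Grade 1 and the 127 has no grade, so the maximum shown is Grade 1: the worse value is ignored.
- Subject B's only low value is 127 mmol/L, no symptoms. No grade is assigned, so no sodium toxicity appears in the maximum-grade summary.
- Neither subject meets the entry condition of the grade 2 or higher listing on sodium.

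**Is the empty cell an artefact of reading the PDF?** The row breaks across a page, so this has to be asked. The columns still line up, and the Grade 3 text continues in its own column after the break. The potassium-decrease row is a useful comparison, as its Grade 2 cell is also empty. There, Grade 1 stops at 3.0 and Grade 3 covers 2.5 to below 3.0, so the two meet at 3.0 and no value is lost. An empty Grade 2 cell is thus a pattern of this table, and it leaves a hole only where Grade 3 carries a symptom condition.

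**Do other planned criteria cover it?** Protocol 8.8.4 promises summaries of values meeting specified criteria, including the numeric examples in Protocol 7.2. Those concern leukocytes and their subsets, AST/ALT (with bilirubin or INR) and creatinine clearance. Sodium is not among them.

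**The case against.** The best case against the point is that it is narrow. Sodium is not among the special-interest laboratory parameters in SAP 3.7.3.1, nor among the laboratory abnormalities of concern in Protocol 7.2. A low result would still be visible in the raw-value and change-from-baseline summaries, the shifts against the normal range, the out-of-range flags and the listing of all abnormal values. Nothing in the documents suggests that such values will be frequent. All of this stands. It limits the weight of the point but does not supply the missing grade. Loss of a cell in PDF reading cannot be wholly excluded, though the layout makes it unlikely.

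Three stronger readings are tempting and are not supported:

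- **That every value of 125-129 goes ungraded because laboratory data carry no symptom field.** The SAP does not say how symptoms are determined, and adverse events are recorded throughout the study. Symptom status could be taken from that record. The gap is established only for the symptom-free case.
- **That grading phosphate is an error.** Phosphate is absent from the chemistry panel in Protocol 6.4.12, which starts "Chemistry samples will be analyzed for the following: sodium, potassium, calcium, magnesium, chloride, bicarbonate, glucose, blood urea nitrogen, creatinine" and ends "total protein, albumin, alkaline phosphatase, lactate dehydrogenase, ALT, AST, gamma-glutamyl transferase, and creatine phosphokinase". A row with no data changes no result, however, and the same section allows additional discretionary testing.
- **That the table wrongly omits creatine kinase and lipids.** SAP 3.7.3.1 lists lipids and "Creatinine Kinase" (presumably the protocol's creatine phosphokinase) as of special interest, both are collected, and neither has a row in SAP 5.8. But the SAP nowhere says that special-interest parameters must be graded. It gives them their own summaries, and the table is selective: magnesium, glucose and lactate dehydrogenase are collected and have no row either. Grading them is a preference about coverage.

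**Conclusion.** The point holds for the sodium-decrease row. As printed, a symptom-free sodium of 125-129 mmol/L has no grade, between a Grade 1 band above and a Grade 3 band below. Such a result is missing from or understated in the maximum-grade summary and absent from the grade 2 or higher listing, while remaining visible in the ungraded laboratory outputs. The size is one band of five whole-number values in one analyte. The number of subjects affected cannot be estimated from the documents.

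The conclusion assumes that the empty Grade 2 cell is empty in the source document, that the LLN is at least 130 mmol/L, and that the row is applied as written. It has no bearing on the primary efficacy analysis or on the definitions of adverse events of special interest. It is worth correcting because the rule as stated gives a wrong safety output and the correction is trivial.

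**What to change.** In SAP 5.8, sodium decrease, enter in the Grade 2 cell: 125 to below 130 mmol/L, not documented as symptomatic. Grade 2 is the only open grade between the printed Grade 1 and Grade 3. Add one sentence saying that symptom status is taken from the adverse event record, with the matching rule (which terms, and how close in time to the sample). The sponsor should check the entry against the CTCAE version named in the table heading.

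The alternative is to grade all of 125-129 mmol/L on the value alone and to state which grade applies. This is simpler to program and needs no link to adverse events. Its small drawback is that it departs from the printed symptom condition: Grade 2 would understate symptomatic cases and Grade 3 would overstate symptom-free ones.

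If sodium can be reported with decimals, write the Grade 3 limits as continuous bounds too, since 124.5, for example, lies between the printed integer limits.

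The cost is one table cell, one sentence and the matching program line, with no new data. Deleting the phosphate row is optional tidying. Grading creatine kinase and lipids is also optional; if it is not done, a line saying that they are summarised but not graded would avoid the question.
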